4.4. Randomized intervention

The randomized interventions will be the following (in random order, separated by a 1-week \pm 3 day washout period)

- Potassium nitrate: Interventional drug capsules will consist of potassium nitrate (KNO₃-) crystals [610 mg, corresponding to 6.03 mmoles of NO3-] with 190mg of lactose monohydrate, spray dried, NF. The dose for this trial will be 18 mmoles of NO₃-per day, given as one capsule (6 mmoles) three times a day.
- Control: Capsules will consist of potassium chloride (KCl), granular, USP (450mg) plus lactose monohydrate, spray dried, NF (300mg). We chose potassium chloride as the control in order to isolate the effects of nitrate from any potential effect of potassium supplementation. The dose for this trial will be 18 mmoles of KCl per day, given as one capsule (6 mmoles) three times a day.

5. STUDY VISITS AND PROCEDURES

An overview of the study design and flow of study visits is presented in Figure 3.

The following investigational devices will be used during the study:

Portalite: continuous wave near infrared spectroscopy (NIRS) system to measure oxygenation of muscle tissue

Portamon: continuous wave near infrared spectroscopy (NIRS) system to measure oxygenation of muscle tissue

5.1. Initial Visit

During the baseline study visit, inclusion and exclusion criteria will be reviewed to ensure subject suitability. After eligibility has been confirmed, written informed consent will be obtained from the subject using Institutional Review Board (IRB)-approved documents. Informed consent will be

obtained before any study procedures. Subjects will be given the opportunity to have all questions regarding their participation answered in detail in a private setting before entering the study.

Following informed consent, a physical examination, with measurement of orthostatic blood pressures, will be performed. A urine pregnancy test will be performed in women with childbearing potential. Blood will be collected for measurement of (a) comprehensive metabolic panel; (b) complete blood count; (d) methemoglobin. A pregnancy test (for women of childbearing potential) and Glucose-6-phosphate dehydrogenase (G6PD) deficiency screening (for males of males of African, Asian or Mediterranean decent) will be performed as needed. Blood, urine, and saliva samples will be collected and frozen for nitrate/nitrite and biomarker level determination. The Kansas City Cardiomyopathy Questionnaire (KCCQ) will be administered. Subjects will also be given an informational brochure regarding foods that are high in nitrate/nitrite and thus should be avoided during the study.

Echocardiography will then be performed using a standardized protocol. Images will be obtained from the parasternal long axis, short axis, apical 5-, 4-, 3-, and 2-chamber, subcostal, and suprasternal views for offline analysis of myocardial strain. Dedicated ventricular chamber images will be obtained in the 4- and 2-chamber apical positions for determination of left ventricular volumes. Mitral inflow velocities, including color M-mode interrogation, will be assessed in the 4- chamber view. Tissue Doppler imaging will be performed at the mitral septal position, approximately 1-cm apical to the mitral valve plane. Additional images will be obtained in the parasternal short axis at the level of the papillary muscles, 2-chamber, and 4 chamber apical views for assessment of myocardial strain. Pulse-wave Doppler interrogation of the left ventricular outflow tract (LVOT) will be performed in the apical 5-chamber view.

Concurrent arterial tonometry will be performed using a high-fidelity tonometer at the carotid, femoral, and radial arteries, using a Sphygmocor device. Waveforms will be calibrated using the brachial artery blood pressures, obtained using a validated oscillometric device. Waveforms will be digitally-stored for off-line analysis. Where available, we will also measure blood pressure using a BP+ device (Uscom, Sydney, Australia), which is an FDA-approved device that measures brachial and central blood pressure using a standard brachial blood pressure cuff. Body surface measurements will be made to determine distance between the suprasternal notch to the carotid, radial, and femoral arteries. A 6-Minute Walk Test will also be performed during this visit. Patients who demonstrate significant desaturation during exercise $\leq 94\%$ or a fall in Spo2 $\geq 5\%$) will be discontinued from the study at this timepoint.

Initial visit procedures

- Informed consent*
- Eligibility assessment
- Medical history, review of concomitant medications
- Dietary counseling
- KCCQ
- Physical Exam (including orthostatic and anthropometric measurements)
- ECG, laboratory tests (CBC, comprehensive metabolic panel, NTproBNP, methemoglobin; pregnancy test and G6PD deficiency screening as needed
- Blood, urine, saliva collection
- Echocardiogram, arterial tonometry

• 6 minute walk test with oxygen saturation

* Informed consent will be obtained before any study procedures

5.2. Randomization procedure

A blocked randomization will be performed. Each block will contain an equal number of allocations to KNO₃ followed by KCI versus KCI followed by KNO₃. The order of treatment sequences within each block will be randomized.

5.3. Intervention Phase 1

Subjects will be randomized to receive either active drug (KNO₃) or control (KCI) as the "first" drug for phase A. The initial dose will be one 6 mmol capsule administered twice daily, to be taken with meals. We will provide subjects with a 14-day supply of study medication to account for potential delays in receiving the 2nd batch of medication (i.e., after the 1-week call).

1-week call: Subjects will be called by telephone ~1 week later to assess if they are experiencing any side-effects. Subjects will receive reinforcement of the dietary restrictions imposed during the study. Subjects will be interrogated about headaches and dizziness. If these symptoms are not present, or are not worse compared to the subject's baseline, the drug dose will be up titrated to 18 mmol daily (One 6-mmol capsule taken 3 times per day). The presence of orthostatic symptoms (i.e. sustained lightheadedness upon standing) will prompt a visit to assess for orthostatic vital signs. The presence of symptomatic orthostatic hypotension (20 mmHg reduction in systolic blood pressure with associated symptoms such as dizziness) measured at this subsequent assessment visit will prompt exclusion of patients from the trial.

For subjects who have a serum K at the initial visit between 4.7 and 5.0 mEq/L in the presence of either: (a) potassium-sparing diuretic use, or (b) Estimated glomerular filtration rate of 30-39 mL/min/1.73m2, we will check a serum potassium 1 week after the implementation of the 18 mmol/d dose as a safety measure. A serum potassium > 5.5 mEq/L will prompt exclusion at this point.

At 3 weeks into each interventional phase, the Actigraph devices will be mailed to the subjects. The goal will be for the subjects to wear this device on their wrist during the final week of each interventional phase to look for differences with each therapy. The devices will be brought back by the subject at the endpoint visit.

Phase 1 endpoint assessment: Following 4 ± 1 weeks of therapy with KNO₃/KCl, subjects will return for endpoint assessments. Physical examination with measurement of orthostatic blood pressure, KCCQ, dietary counseling, and side effect assessments will be performed. A urine pregnancy test will be performed in women with child-bearing potential. An intravenous catheter will be placed in the antecubital vein and securely fixed in place. Blood, urine and saliva samples will be collected prior to, and approximately 2 hours after the morning dose administration, given with a standardized low-nitrate breakfast. Blood RNA samples will be collected prior to the

morning dose administration using Paxgene tubes (BD Biosciences, Franklin Lakes, NJ). Subjects will then undergo repeat echocardiography, arterial tonometry and blood pressure measurements (including BP+ central blood pressure measurements). Subjects will then perform a maximal-effort peak oxygen consumption (VO₂) test using a supine bicycle exercise test with expired gas analysis. Cardiac output at rest will be measured immediately prior to exercise using pulsed wave Doppler echocardiography. Flow-mediated dilation of the brachial artery to assess endothelial function will be performed (Unex Co. Ltd., Nagoya, Japan). An additional blood sample will be obtained at peak exercise. The Kansas City Cardiomyopathy Questionnaire (KCCQ) will be administered. Download of actigraph device data will also be done.

Phase 1 visit

- Interim medical history, review of concomitant medications
- Physical Exam (including orthostatic vital signs)
- Blood, urine, saliva collection
- Blinded drug administration
- ECG, laboratory tests (CBC, comprehensive metabolic panel, methemoglobin; pregnancy test as needed, BD PAXgene RNA samples
- KCCQ
- Blood, urine and saliva collection approximately 2 hours post-administration
- Echocardiogram, arterial tonometry
- Cardiopulmonary test with resting cardiac output measurements, blood draw at peak exercise
- Download of Actigraph data and continuation of outpatient physical activity
- Endothelial function assessment with flow-mediated brachial artery dilation

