5.4. Washout period

Following the endpoint assessment, subjects will enter a 1-week \pm 3 day washout period during which they will not receive any study medications.

At 3 weeks into each interventional phase, the Actigraph device will be mailed to the subjects. The goal will be for the subjects to wear this devices on their wrist during the final week of each interventional phase to look for differences with each therapy. The device will be returned by the subject at the endpoint assessment.

5.5. Intervention Phase 2

Following the washout period, subjects will receive either active drug (KNO₃) or control (KCI) during phase 2 of the trial. Subjects will receive the intervention (KNO₃ or KCI) that was not administered to them in phase 1, such that each subject will receive both study interventions in this cross-over design. The ~1-week call and the ~4-week study visit will be repeated as above. We will provide subjects with a 14-day supply of study medication to account for potential delays in receipt of the 2nd batch of medication (i.e., after the 1-week call).

1-week call: Subjects will be called by telephone ~1 week later to assess if they are experiencingside-effects. Subjects will receive reinforcement of the dietary restrictions imposed during the study. Subjects will be asked about headaches and dizziness. If these symptoms are not present, or are not different than the subject's baseline, the drug dose will be up-titrated to 18 mmol daily (One 6-mmol capsule taken 3 times per day). The presence of orthostatic symptoms will prompt a visit to assess for orthostatic vital signs. The presence of symptomatic orthostatic hypotension (20 mmHg reduction in systolic blood pressure with associated symptoms such as dizziness) at the follow up visit will prompt exclusion of patients from the trial.

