6. DRUG DISPENSING, ACCOUNTABILITY AND DESTRUCTION

 KNO_3 and KCI capsules will be prepared at the University of Pennsylvania Investigational Drug Service [[name]]. Drug bottling, labeling and dispensing will also be managed by the Penn Investigational Drug Pharmacy. Prior to initiation of each phase, participants will receive a sufficient supply of KNO3 or control capsules to last until the end of each treatment phase, allowing for 100% compliance with the regimen for the entire treatment phase, including a window of ± 7 days for the 1-week uptitration (to ensure an adequate supply of medication before additional medications are received by the subject) and ± 1 week for the endpoint assessment visit.

Subjects will be instructed to take the medication as required by the protocol, and compliance will be assessed via pill count performed by IDS.

Subjects will be instructed to return unused capsules at the end of each treatment phase. A pill count will be performed by IDS prior to destruction of the drug. Returned trial capsules will be stored separately from the non-allocated trial capsules until returned trial capsules are disposed of. The IDS personnel will keep track of all received, used, partly used and unused trial products.

Used and unused study drug will be destroyed at the instruction of the sponsor. A copy of the drug destruction SOP should be maintained in the pharmacy section of the Regulatory Binder. Study drug should not be destroyed until drug accountability has been completed.

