- Stomach discomfort
- Slight headache
- Dizziness
- Lightheadedness
- Low blood pressure
- Stomach Ache, diarrhea, nausea, or vomiting
- Shortness of breath
- Flushing
- Rash
- Mild orthostatic hypotension
- Clinically significant methemoglobinemia or significant symptomatic orthostatic hypotension (20 mmHg or greater reduction in systolic blood pressure with associated symptom such as dizziness) are potential side effects, although we will consider them unexpected given prior data in this patient population with this particular drug and dosing scheme.

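### In each phase the only scheduled symptom call is made at 12 mmol/d; after the step to 18 mmol/d no symptom or orthostatic check is scheduled for all subjects until the endpoint visit, nominally 21 days later

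*Combined protocol and SAP*

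**What the plan says.** Both phases begin with one 6 mmol capsule twice daily (section 5.3, repeated under section 5.5). In section 5.3: "Subjects will be called by telephone ~1 week later to assess if they are experiencing any side-effects". The caller asks about headache and dizziness, and the answer decides the dose: "If these symptoms are not present, or are not worse compared to the subject's baseline, the drug dose will be up titrated". The new dose is one capsule three times daily. Section 5.5 repeats the call and the step in phase 2. Both sections attach a trigger to the call, in section 5.5 worded as "The presence of orthostatic symptoms will prompt a visit to assess for orthostatic vital signs". A symptomatic systolic fall of 20 mmHg at that visit takes the subject out of the trial.

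After the step, the plan contains the following:

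- For a subset defined by baseline potassium of 4.7 to 5.0 mEq/L plus a potassium-sparing diuretic or eGFR of 30 to 39, section 5.3 says "we will check a serum potassium 1 week after the implementation of the 18 mmol/d dose as a safety measure".
- At week 3 an Actigraph is mailed to every subject. No symptom question is described with it.
- At 4 ± 1 weeks comes the endpoint visit: "Physical examination with measurement of orthostatic blood pressure, KCCQ, dietary counseling, and side effect assessments will be performed". Sampling is then tied to that day's dose: "Blood, urine and saliva samples will be collected prior to, and approximately 2 hours after the morning dose administration".
- Section 11.3.3 sets the repeat blood pressure at 4 ± 1 weeks, and adds a measurement whenever a subject reports an orthostatic symptom.
- The adverse event row of Appendix 1 is marked only at week 1 and at 4 ± 1 weeks of each phase.

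Section 6 sizes the drug supply for a step that may move, "including a window of ± 7 days for the 1-week uptitration". Section 7.2 lists dizziness, lightheadedness, low blood pressure and "Mild orthostatic hypotension" among the potential expected effects of KNO₃. Section 5.6 requires a log of all adverse events. Section 7.3 captures serious events from consent to the final visit. Section 13 places the data and safety monitoring plan in Appendix 3, which is not in the supplied text.

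**The concern.** The week 1 call tests tolerance of 12 mmol/d, and a clear answer raises the dose. Nobody is scheduled to ask the same question at the higher dose until the phase is practically over. Testing the safety of KNO₃ is a stated purpose (section 1), and 18 mmol/d is the trial dose (section 4.4).

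Two things are at stake:

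- Between the step and the endpoint visit, the exclusion rule for symptomatic orthostatic hypotension depends on the subject volunteering a symptom. At the endpoint visit, in the order listed, the orthostatic check precedes the morning dose and the exercise test, but only the visit-day dose of that phase remains. A finding in phase 1 still protects phase 2, but it protects little of phase 1.
- Non-serious symptoms at the target dose are first asked about late, and by recall.

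The protocol already uses a one-week interval twice: for symptoms after the first dose, and for potassium after the step in the subset. It does not use it for symptoms after the step.

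**Working it through.** The plan gives no figure on this point to reproduce. The check is calendar arithmetic.

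**Inputs**

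- Call at about day 7 (sections 5.3, 5.5).
- Step day *s*: day 7 if on time. The late case is an assumption: 7 + 7 = day 14, taken from the supply allowance in section 6, which is not stated as a visit window.
- Endpoint visit day *e*: 4 ± 1 weeks, so 21, 28 or 35.
- Proposed extra call at *s* + 7.

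**Formulas**

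- Days at 18 mmol/d before the next scheduled question = *e* − *s*
- Days by which the extra call brings that question forward = *e* − (*s* + 7)

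| Step day | Endpoint day | Days at 18 mmol/d before next question | Days gained by the call |
|---|---|---|---|
| 7 | 21 | 14 | 7 |
| 7 | 28 | 21 | 14 |
| 7 | 35 | 28 | 21 |
| 14 (assumed) | 21 | 7 | 0 |
| 14 (assumed) | 28 | 14 | 7 |
| 14 (assumed) | 35 | 21 | 14 |

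With an on-time step, the wait as a share of the phase is 14/21 = 67%, 21/28 = 75% and 28/35 = 80%.

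**Subjects held at 12 mmol/d.** They too are next asked at the endpoint visit, 14, 21 or 28 days after the day 7 call. A call at day 14 gains 7, 14 or 21 days.

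**Size of the step.** 2 × 6 = 12 and 3 × 6 = 18 mmol/d; 18/12 = 1.5. The daily dose rises by half, but the amount per intake stays at 6 mmol.

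**Exposure against the cited pharmacokinetics study.** Section 11.2.1 describes 2 weeks (14 days) of dosing. If all 14 days were at 18 mmol/d, the ratio for subjects who step up runs from 7/14 = 0.5 to 28/14 = 2.0. That assumption is doubtful, because the section reports both 12 and 18 mmol/d; time at 12 would raise the ratio. The range straddles 1, so it carries no weight here.

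**Number of extra calls.** One per subject per phase: 22 × 2 = 44 at most. With the 90% retention of section 10.1, 22 × 0.90 = 19.8, about 20 subjects, and 20 × 2 = 40.

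These are times and counts, not risks. The documents give no event rate for post-AVR subjects at this dose.

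**The case against.** The strongest reply is that the risk has already been screened down:

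- Section 11.3.3 enrols subjects with supine systolic pressure above 110 (section 4.3.2 puts the lower limit at 100) and excludes a standing fall of more than 20 mmHg.
- Section 4.3.2 excludes organic nitrates and phosphodiesterase inhibitors that cannot be withheld.
- Section 4.3.1 requires 30 days without changes in antihypertensives, and section 5.8 discourages changes during the study.

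The pharmacokinetics data point the same way: a pressure fall of about 12 mm Hg without symptoms, no fall in ambulatory pressure, no clinically significant methemoglobin rise at either dose (section 11.2.1), and no side effects (section 11.3.3). The step leaves each intake at a size the subject has already taken for a week. Symptomatic hypotension is by definition noticeable, subjects are advised of the risks, and any report at any time triggers a measurement.

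Most of this stands, and it makes the point a modest one. It does not close the gap. The reassuring data come from 2-week dosing; the study's title (reference 127) names HFpEF, although section 11.2.1 calls it the same population and section 11.3.3 a similar one. Nor did the protocol rely on self-report alone at 12 mmol/d.

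Three stronger readings are tempting, and the documents do not support them:

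- *Subjects are unmonitored after the step.* They are not. Self-reports trigger measurements, all adverse events are logged (section 5.6), and the site investigator must see that they are noted and followed (section 7.3). What is missing is a scheduled question.
- *Section 11.2.1 contradicts the schedule.* It undertakes to check blood pressure for safety over the whole study, but refers to the next section for the detail. Section 11.3.3 then sets the scheduled repeat and the symptom-triggered measurements. One on-treatment visit per phase is sparse, but it is not a contradiction.
- *The KNO₃ versus KCl comparison is biased.* The schedule is identical in both blinded phases, so nothing in it favours either treatment.

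**Conclusion.** The point holds as a monitoring gap of modest weight, somewhere between an optional improvement and a low-priority recommendation. On the supplied text, the only scheduled symptom call in each phase is made at 12 mmol/d, and no symptom or orthostatic check is scheduled for all subjects between the step and the endpoint visit. The time at 18 mmol/d without one is nominally 21 days: 14 to 28 with an on-time step, and 7 to 21 if the step slips to day 14.

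This rests on three assumptions: the call and step fall near day 7, or near day 14 if the supply allowance is fully used; the Actigraph mailing includes no symptom enquiry, since none is described; and Appendix 3 adds no contact, which could not be checked. The risk is probably low and cannot be quantified from the documents. It would go too far to infer that the dose is unsafe or that exposure exceeds what the pharmacokinetics study covered.

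**What to change.** Repeat the same scripted side-effect call in both phases, about 1 week after 18 mmol/d starts. Subjects held at 12 mmol/d because headache or dizziness worsened should get it at about week 2, since they face the same wait. Apply the existing orthostatic-visit trigger and exclusion rule to the answers. If a late step puts the call at the endpoint visit, let the visit replace it.

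Check Appendix 3 first. If it already has such a contact, only Appendix 1 needs the entry. Otherwise add the call to sections 5.3 and 5.5 and to the adverse event row of Appendix 1.

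The cost is a small amendment and at most 44 short calls (about 40 at 90% retention) by the staff who already make the week 1 call, plus an orthostatic visit for anyone who reports orthostatic symptoms. Dose, titration, stopping rules, endpoints and analysis stay as they are.

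### The actigraph is posted at week 3 of each phase, yet the visit where it is handed back may fall anywhere from week 3 to week 5, so the intended final week of wear is not secured

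*Combined protocol and SAP*

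**What the plan says.** Section 5.3 sets the dispatch date by the start of the phase: "At 3 weeks into each interventional phase, the Actigraph devices will be mailed to the subjects". It then gives the purpose: "The goal will be for the subjects to wear this device on their wrist during the final week of each interventional phase", in order to compare the two therapies. The device leaves the subject at the end of the phase: "The devices will be brought back by the subject at the endpoint visit". Section 5.4 repeats the week-3 rule for both phases and again ends wear at the visit: "The device will be returned by the subject at the endpoint assessment".

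The date of that visit is a range. For phase 1, Section 5.3 has "Following 4 ± 1 weeks of therapy with KNO₃/KCl, subjects will return for endpoint assessments". Section 5.5 gives the same window for phase 2 and refers to the nominal time: "The ~1-week call and the ~4-week study visit will be repeated as above". Appendix 1 shows 4 ± 1 weeks for both phases and has a row for retrieving the actigraph, but none for sending it.

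Physical activity appears in the Section 2 summary table as an exploratory aim and is not in that table's endpoint rows. The documents give no mail time, no minimum wear or valid-day rule, and no expected spread of visits within the window. Nothing links posting to the booked visit.

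**The concern.** The earliest permitted endpoint visit falls on the day the device is posted. At that edge of the window the schedule can be followed exactly and still yield no activity data. At the nominal visit, exactly 7 days separate posting from return, so every day in the mail comes out of the intended week.

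What is at stake is the comparison of activity between potassium nitrate and potassium chloride. In a crossover that comparison draws its precision from subjects with usable data in both phases, so a short recording in either phase weakens the pair. With 22 randomized and 90% retention assumed in Section 10.1, about 20 completers are expected (22 × 0.90 = 19.8), which leaves little room for loss.

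**Working it through.** The plan states no figure for wear time or actigraph completeness, so there is none to reproduce. The check is date arithmetic.

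**Inputs from the documents.** Posting on day 21 (Sections 5.3, 5.4). Return at a visit on day V, with V from 21 to 35 and nominal day 28 (Sections 5.3, 5.5, Appendix 1). Intended wear of 7 days. About 20 completers (Section 10.1).

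**Assumptions, not in the documents.** Mail time t of 0 to 5 days, with 1 to 3 as the working range. Distribution of V from uniform over the window to clustered at day 28. The two phases independent.

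**Step 1. Wear available.** Wear days = max(0, V − 21 − t).

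| Visit day | t = 0 | t = 1 | t = 2 | t = 3 | t = 5 |
|---|---|---|---|---|---|
| 21 | 0 | 0 | 0 | 0 | 0 |
| 24 | 3 | 2 | 1 | 0 | 0 |
| 26 | 5 | 4 | 3 | 2 | 0 |
| 28 (nominal) | 7 | 6 | 5 | 4 | 2 |
| 31 | 10 | 9 | 8 | 7 | 5 |
| 35 | 14 | 13 | 12 | 11 | 9 |

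A full 7 days requires V ≥ 28 + t. This step needs no assumption about visit spread.

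**Step 2. Share of phases with 2 days or fewer.** This means V ≤ 23 + t. Let p be the probability of that event.

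- Uniform over 15 days: t = 1 covers days 21 to 24, p = 4/15 = 0.267; t = 3 covers days 21 to 26, p = 6/15 = 0.40.
- Normal weights centred on day 28 with SD 2 days, exp(−(V − 28)²/8), which total 5.01 over the window: t = 1, p = 0.193/5.01 = 0.038; t = 3, p = 1.124/5.01 = 0.224.

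**Step 3. Completers with 2 days or fewer in at least one phase.** Expected number = 20 × [1 − (1 − p)²].

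| Visit spread | t = 1 | t = 3 |
|---|---|---|
| Uniform | 20 × (1 − 0.733²) = 9.2 | 20 × (1 − 0.60²) = 12.8 |
| Triangular, peak at day 28 | 5.8 | 11.0 |
| Normal, SD 3 days | 4.4 | 10.3 |
| Normal, SD 2 days | 20 × (1 − 0.962²) = 1.5 | 20 × (1 − 0.776²) = 8.0 |

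The range is about 1.5 to 13 of 20. Across the same four spreads, same-day delivery gives 0.5 to 7.2 and 5 days in the mail gives 15.6 to 16.8. If a subject's two visits fell on the same day of the window, the count would be 20 × p, that is 20 × 0.038 = 0.8 to 20 × 0.40 = 8.0 for t of 1 to 3, with both phases short in those subjects.

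**Step 4. Share of phases below the intended 7 days** (V < 28 + t). Uniform: 8/15 = 53% at t = 1 and 10/15 = 67% at t = 3. Normal with SD 2: 60% and 90%. Clustering at day 28 nearly removes the phases with no wear at all (0 to 4%, against 13 to 27% under uniform visits), but it does not restore the full week.

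**The case against.** A reader might infer that many subjects will have little or no activity data. The documents do not support that. It depends on the visit spread and the mail time, and neither is stated. Section 5.5 speaks of a visit at about 4 weeks, so the ± 1 week reads more naturally as a scheduling tolerance than as a uniform spread. At the nominal visit with 1 to 3 days in the mail a subject still has 4 to 6 days of recording, and visits in week 5 can give a week or more. No text requires 7 valid days for a recording to count.

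Three further points are fair. Final-week wear is worded as a goal, so losing some days at an on-time visit is a shortfall against an aim and not a breach of a rule. Section 10.2 describes a mixed model that keeps data from dropouts, so a subject with one usable phase is not automatically discarded, although such a subject adds little to a within-subject contrast. And the stakes are low: one exploratory aim.

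All of this limits the size of the point. None of it removes the conflict in dates. A day-21 visit gives zero wear however fast the mail is, an on-time visit gives the full week only with same-day delivery, and no other section ties dispatch to the booked visit.

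**Conclusion.** The point holds as a minor one. Followed exactly, the week-3 posting rule leaves no wear time at the early edge of the permitted visit window and less than the intended week at the nominal visit unless delivery is same-day. Those two statements rest only on the protocol's own dates. The count of affected subjects, about 1.5 to 13 of 20 completers with 2 days or fewer in at least one phase, rests on assumed mail times of 1 to 3 days, assumed visit distributions and independence between phases. It should be read as a range and not as a forecast. The consequence is confined to the exploratory comparison of physical activity; no primary, secondary or safety result is affected.

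**What to change.** In Sections 5.3 and 5.4, replace the fixed week-3 posting with dispatch timed so that the device reaches the subject at least 8 days before the booked endpoint visit. Posting day is then V − 8 − t. For a visit booked on day 21 that is day 13 with same-day delivery and day 8 with 5 days in the mail. All 7 wear days are then available at every permitted visit date. Define the analysis window as the 7 days before the visit, so that both phases are measured over the same interval. It would help to add a minimum number of valid days and a dispatch row in Appendix 1.

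A simpler alternative is to hand the device out earlier in the phase, for example when the second batch of capsules is supplied. Section 5.3 provides a 14-day first supply; a device in hand by day 14 leaves 21 − 14 = 7 days before even the earliest visit. The protocol does not say how that second batch reaches the subject, so this route needs agreement with the pharmacy.

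The cost is small but not nil. Beyond the wording change, devices stay with subjects somewhat longer, so a few more may be needed or lost, and visits must be booked early enough to set the dispatch date.
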